Dosing Period 2: Dosing Period 2 will last for approximately 2 weeks (Day 29 to Day 43) and includes Visit 9, 10, 11, 12, 13, and 14. Subjects will return to the clinic for Visit 9, 11, and 13 for safety and efficacy assessments. At Visit 9, following the administration of safety and efficacy assessments, subjects initially randomized at Baseline to placebo or to 7mg/kg of UCB7665 will be rerandomized 1:1 to receive either 3 doses of 7mg/kg or 3 doses of 4mg/kg administered by a 30 minute sc infusion at weekly intervals (Visit 9, 11, and 13). The interactive response technology (IRT) will stratify the rerandomization based on the treatment received in Dosing Period 1. At each weekly clinic visit in Dosing Period 2 (Visits 9, 11, and 13), subjects will be required to remain in the clinic/hospital for at least 4 hours safety monitoring postdose period as determined. Subjects may leave the clinic/hospital once the safety monitoring postdose period is over and the investigator or designee has no safety concerns. A follow-up telephone call will be conducted 24 hours post dose to assess the status of the subject (Visits 10, 12, and 14).

Observation Period: All subjects must be followed for 8 weeks after the final dose of IMP is administered. Subjects will return to the clinic for Visits 15, 16, and 18 for efficacy and for safety assessments. Subjects will either return to the clinic/hospital, or, if possible and agreed by investigator and subject, have home visits conducted by certified healthcare professionals, for Visits 17, 19, and 20. The Observation Period begins the day after the final dose of IMP (ie, Visit 13, Day 43); Visit 15 (Day 50) is the first visit in the Observation Period.

Figure 2–1 presents a schematic diagram of the study design.

Figure 2–1: Schematic diagram

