3.2.2 Study periods

The maximum duration of the study per subject will be approximately 18 weeks, consisting of the following 3 periods:

- Screening Period: 1 to 28 days
- Treatment Period: 6 weeks
 - Dosing Period 1 of 4 weeks. This period will start at the first actual dosing of Period 1.
 - Dosing Period 2 of 2 weeks. This period will start at the first actual dosing of Period 2.
- Observation Period: 8 weeks

The end of the study is defined as the date of the final clinic/hospital visit of the final subject in the study.

In the case a subject does not receive dosing in Dosing Period 2, the rule for entering the Observation Period given in [Section 2.3](#) will be generalized such that the subject will enter the Observation Period the day after the last dosing of Dosing Period 1. All data up to the missed dose will be treated according to plan, including data planned on the dosing day prior to the actual dosing.

The following definitions for starting and entering the study periods will be applied:

- Started period 1 is defined as all subjects in the safety set. Completed period 1 includes those subjects who have completed assessments prior to the first study treatment of Period 2 (Day 29).
- Started period 2 is defined as having received treatment on Period 2 Day 29. Completed period 2 includes those subjects who have completed assessments on Observation Period Day 50.
- Started Observation Period is defined as having assessments on Observation Period Day 50. Completed observation period includes those subjects who have a completed status in the study termination case report form

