11.1 Extent of exposure

All drug administration details (including date, start and stop time of infusion, location of infusion site, interruptions, discontinuations, body weight, dose, volume delivered, percent of planned dose) will be listed using the SS. The reasons for any interruptions or discontinuations will be included in the listing. The duration of the infusion, in minutes, will also be calculated.

The percent of planned dose administered will be calculated based on the actual volume delivered as follows:

$$\text{Percent of planned dose (\%)} = (\text{Actual volume}/\text{Planned volume}) * 100$$

For all subjects the planned volume is 10mL.

In Dosing Period 1 subjects will be randomized (1:1) to receive one of the following treatments:

- 3 sc doses of UCB7665 7mg/kg at 1 week intervals
- 3 sc doses of placebo at 1 week intervals

In Dosing Period 2 subjects will be rerandomized (1:1) to receive one of the following treatments:

- 3 sc doses of UCB7665 7mg/kg at 1 week intervals
- 3 sc doses of UCB7665 4mg/kg at 1 week intervals

The randomization in Dosing Period 2 will be stratified by the treatment received in Dosing Period 1.

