11.2 Adverse events

Adverse events will be recorded from the time of informed consent until study completion. All AEs will be coded ([Section 3.8](#)) and categorized by relationship to UCB7665.

In addition, AEs will be classified according to the Common Terminology Criteria for Adverse Events (CTCAE) Version 4.03 for severity. For any AEs where it is not possible to provide a CTCAE grading, the events will be assessed using a standard intensity classification (mild, moderate and severe).

A TEAE is defined as any event that was not present prior the first administration of IMP or any unresolved event already present before the first administration of IMP that worsens in intensity following exposure to treatment. Adverse events starting before the first administration of IMP or after 8 weeks following the final dose of IMP will not be considered TEAEs. Thus AEs before first dosing and AEs after 8 weeks following the final dose will be combined in one category. Such events will be listed only.

Where dates are missing or partially missing, AEs will be assumed to be treatment-emergent. Handling of missing dates/times for classification of AEs as TEAEs is described in [Section 4.2.7](#).

The following rules will be used to assign a TEAE to a study period:

- Dosing Period 1: a TEAE will be assigned to Dosing Period 1 for the tabulations if the start date/time of the event is at the time of or after the first administration of IMP on Day 1, up to the time of actual first administration of IMP in Dosing Period 2 (planned for Day 29)
- Dosing Period 2 or Observation Period: a TEAE will be assigned to 'Dosing Period 2 or Observation Period' for the tabulations if the start date/time of the event is at the time of or after the first administration of IMP (planned for Day 29), until 8 weeks following the final dose; events starting later than 8 weeks following the final dose of IMP are not considered TEAEs

In the case of early withdrawal in either Dosing Period 1 or 2, a TEAE will be assigned to the respective Dosing Period based on the last received infusion.

The number and percentage of subjects who experience TEAEs will be summarized for each Dosing Period and treatment group. In all tabulations, TEAEs occurring during the Observation Period will be presented as part of Dosing Period 2. In addition summaries for total active and all treatments will be created. The following summaries will be presented:

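### Adverse event columns covering about 10 to 14 weeks sit beside 4-week Period 1 columns as crude percentages, and the total active column is undefined

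*SAP*

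**What the plan says.** SAP 11.2 assigns treatment-emergent events to two blocks. The first runs from the first dose to the first actual Period 2 dose, planned for Day 29. The second runs from that dose "until 8 weeks following the final dose; events starting later than 8 weeks following the final dose of IMP are not considered TEAEs". The Observation Period has no column of its own: "In all tabulations, TEAEs occurring during the Observation Period will be presented as part of Dosing Period 2".

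On pooling, the SAP says only "In addition summaries for total active and all treatments will be created". It does not say which periods or subjects make up total active.

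Each table reports the number of subjects with an event, that number as a percentage, and a count of events. No subject-time denominator appears in SAP 11.2 or in protocol 14.4.1. SAP 11.1 lists administration details but plans no summary of time at risk.

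Three parts of the plan limit the problem:

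- The introduction to SAP 11 puts the Period 1 columns, placebo and 7mg/kg, first.
- SAP 11.2 lists one additional table restricted to events in the dosing period.
- The adverse event listing shows days since the first and the most recent dose.

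**The concern.** After Day 29 no further placebo is given: "In Dosing Period 2 subjects will be rerandomized (1:1) to receive one of the following treatments", and both options are active doses. Planned placebo time therefore ends at the Period 2 dose, while active and off-drug time runs on to the final visit. SAP 11.2 sorts the tables by the frequency in a Period 2 column, which shows that columns from both periods share a table. A crude percentage rises with the length of its window, so columns of 4, 10 and 12 weeks cannot be read across without an allowance for time.

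Safety and tolerability is a secondary objective (protocol 3.2). Protocol 5.4.1 also wants the subjects who receive six active doses to inform safety over extended dosing. Two readings are at risk: pooled active against placebo, and the continued 7mg/kg column in Period 2 against the 7mg/kg column in Period 1. Either could show an excess that comes only from longer follow-up.

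**Working it through.** **Plan's own figure.** Screening up to 4 weeks + treatment 6 weeks + observation 8 weeks = 18 weeks, the stated maximum. Last dose on Day 43 + 56 days = Day 99, which matches Visit 20 in the protocol.

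**Windows** (SAP 2.3, 3.2.2 and 11.2). SAP 3.2.2 gives "Dosing Period 1 of 4 weeks. This period will start at the first actual dosing of Period 1".

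- Period 1 columns: 29 − 1 = 28 days = 4 weeks.
- Period 2 columns, including observation: 99 − 29 = 70 days = 10 weeks.
- Subjects on 7mg/kg from Day 1, both periods: 99 − 1 = 98 days = 14 weeks.
- Total active over both periods: with 1:1 allocation of about 42 subjects, half have 10 weeks and half 14. The mean is 12 weeks, three times the placebo window.

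**Illustration 1: the same constant hazard in every column.** The documents give no event rate, so the 4-week incidence p is an assumption. Incidence over t weeks is 1 − (1 − p)^(t/4). The both-period pool is the mean of the 10-week and 14-week values.

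| p at 4 weeks | 10 weeks (Period 2 pool) | 14 weeks | Both-period pool | Ratio of both-period pool to p |
|---|---|---|---|---|
| 5% | 12.0% | 16.4% | 14.2% | 2.85 |
| 10% | 23.2% | 30.8% | 27.0% | 2.70 |
| 20% | 42.8% | 54.2% | 48.5% | 2.42 |
| 30% | 59.0% | 71.3% | 65.2% | 2.17 |
| 50% | 82.3% | 91.2% | 86.7% | 1.73 |

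For p = 20%: 1 − 0.8^2.5 = 0.4276, 1 − 0.8^3.5 = 0.5421, mean 0.4848. In subjects that is about 4 of 21 on placebo against 20 of 42 in the pool, with no true difference.

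**Illustration 2: events only in the week after each dose.** Let p now be the risk over three doses. Placebo subjects have three dosed weeks. In the both-period pool, half the subjects have three dosed weeks on active and half have six. The ratio is [p + 1 − (1 − p)²] / (2p) = (3 − p)/2.

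- p = 5%: 1.48
- p = 10%: 1.45
- p = 20%: 1.40
- p = 30%: 1.35

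If total active meant Period 2 only, both sides would have three dosed weeks and the ratio would be 1.

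**Check on a simple rate correction.** Keep the dose-linked assumption and equal risk per dose, and divide by all subject-weeks. Dosed weeks make up 3/4 = 0.75 of placebo time, but only (6 + 3)/(14 + 10) = 9/24 = 0.375 of pooled active time. For rare events, active would then appear to have half the placebo rate although the risk per dose is equal.

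**The case against.** The strongest reply is that the fair comparison is already the main display. Period 1 placebo and 7mg/kg are randomised, cover the same 4 weeks and come first in every table. The pooled columns are additional, and nothing in either document tests total active against placebo. This stands. A reader might infer that the placebo-controlled safety comparison as a whole is biased; the documents do not support that.

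A second reply is that the 12-week mean depends on an unstated definition. This also stands. Pooling across periods is the natural reading, because Period 1 has one active arm and no placebo is dosed in Period 2. It is not the only reading, because the SAP keeps a placebo group in the later block for subjects not dosed in Period 2. The range therefore has to cover both definitions.

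A third reply is that constant hazard through eight drug-free weeks is a strong assumption, particularly for headache and gastrointestinal events if these follow infusions. That is why the lower ratio is shown. A reader might also infer that real signals could be hidden. In crude cumulative percentages there is no mechanism for this, since longer follow-up can only raise the figure.

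Finally, placebo time is not strictly capped at Day 29. Subjects who stop in Period 1 have later events assigned by their last infusion and can contribute more than 4 weeks. Few subjects are likely to be affected.

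What the replies leave open is that the SAP neither defines the pooled column nor tells the reader which columns can be compared. The single dosing-period table does not cover the tables of serious events or events of interest, and its scope is unclear beside the rule that observation events go into Period 2 in all tabulations.

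**Conclusion.** The point holds as a presentation problem confined to the Period 2 and total active columns. Under equal constant rates, a 4-week incidence of 20% would appear as about 43% (Period 2 pool) to 48% (both periods). For dose-linked events the both-period ratio is about 1.35 to 1.5, and there is no excess if the pool is Period 2 only. The windows come from the documents; the event rates and hazard shapes are assumptions. The randomised Period 1 comparison is unaffected. Minor severity.

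**What to change.** Amend SAP 11.2 as follows:

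1. Define total active: which periods and subjects it pools, and its denominator.
2. State, in the text and as a table footnote, that the placebo comparison is the Period 1 columns only.
3. In the main treatment-emergent, serious, and events-of-interest tables, show Period 2 dosing-window events separately from later Observation Period events. Define where that window ends and reconcile it with the existing dosing-period table. This needs care: SAP 2.3 starts the Observation Period the day after the last dose, whereas SAP 6.4.4 runs Dosing Period 2 to 7 days after it for medications. The first cut would move events in the week after the third dose into observation.
4. Report subject-time at risk for each column.
5. Give any exposure-adjusted incidence by these same windows, not only over the whole active and off-drug span, because drug-free follow-up would dilute infusion-linked events.

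The cost is some programming and longer tables. Event onset and dosing dates and times are already collected, so no new data or change in conduct is needed.

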11.3 Clinical laboratory evaluations

Laboratory data (chemistry, hematology and urinalysis) and changes from Baseline (if applicable) for numeric variables will be summarized by treatment group and time point. Any laboratory measurements that are BLQ or ALQ will be handled as described in Section 4.2.2. Values outside the reference range for the numeric variables will be flagged in the listings. The reference ranges will also be reported in the listings. In addition, the listings will include a flag for values identified as treatment-emergent markedly abnormal (TEMA)/potentially clinically significant (PCS) as defined by the criteria outlined in Table 14-7.

Chemistry, hematology and coagulation parameters will be summarized by treatment group at each time point, for both absolute values and changes from Baseline.

The laboratory variables are presented in Table 11–1. For selected laboratory variables that are identified in Table 11–1, the change in category from Baseline will be presented in shift tables at each post-Baseline assessment.

Table 11–1: Clinical laboratory measurements

Category	Panel	Variable
Hematology	Red blood cell	RBC count, hemoglobin, hematocrit, HbA1c
	Platelet	Platelet count ^a
	White blood cell	WBC count
	White blood cell differential	Absolute counts: ANC, basophils, eosinophils, ALC, monocytes Percentages: neutrophils/leukocytes, basophils/leukocytes, eosinophils/leukocytes, lymphocytes/leukocytes, monocytes/leukocytes
Chemistry	Electrolytes	Sodium, chloride, potassium, calcium, phosphate, magnesium
	Enzymes	Amylase, Creatine kinase
	Hormones	procalcitonin
	Kidney function	Urea-N, creatinine ^a
	Proteins	Total protein, albumin ^a , alpha- and beta- globulins, hsCRP ^a
	Liver function	AST ^a , ALT ^a , GGT, ALP, LDH, total bilirubin, direct bilirubin (if indicated)

Table 11–1: Clinical laboratory measurements

Category	Panel	Variable
	Lipids	Total cholesterol, LDL cholesterol, HDL cholesterol, triglycerides
Urinalysis	Dipstick	pH, protein, glucose, ketones, urobilinogen, bilirubin, blood, nitrite, leucocytes
	Quantitative	Albumin, creatinine, protein
	Sediment	Leukocytes

^a Shift table will be created for these variables

ALC=absolute lymphocyte count; ALP=alkaline phosphatase; ALT=alanine aminotransferase; ANC=absolute neutrophil count; aPTT=activated partial thromboplastin time; AST=aspartate aminotransferase; BUN=blood urea nitrogen; GGT=gamma-glutamyltransferase; HbA1c=glycosylated hemoglobin; HBsAG=hepatitis B surface Antigen; HCV Ab=hepatitis C virus antibody; HDL=high density lipoprotein; hsCRP=high sensitivity C-reactive protein; LDH=lactate dehydrogenase; LDL=low density lipoprotein; RBC=red blood cell; WBC=white blood cell.

11.3.1 Potential drug-induced liver injury

A separate listing will present subjects who meet one or more of the following potential drug-induced liver injury (PDILI) criteria at any visit:

- Alanine aminotransferase (ALT) or Aspartate aminotransferase (AST) $\geq 5x$ Upper limit of normal (ULN)
- ALT or AST increase $\geq 3x$ ULN and Total bilirubin $\geq 2x$ ULN
- ALT or AST $\geq 3x$ ULN who exhibit temporally associated symptoms of hepatitis or hypersensitivity
- ALT or AST $\geq 3x$ ULN (and $\geq 2x$ Baseline) and $< 5x$ ULN, total bilirubin $< 2x$ ULN, and no eosinophilia (i.e., $\leq 5\%$), with no fever, rash, or symptoms of hepatitis.

The listing will display only visits for which at least one of the above criteria was fulfilled for a given subject, and will display all results obtained at that visit for the specified parameters.

A summary of subjects who met the criteria for PDILI will be presented together with any additional relevant data collected, if applicable.

11.4 Vital signs, physical findings, and other observations related to safety

11.4.1 Vital signs

The following vital signs measurements will be obtained:

- Pulse rate
- Systolic and diastolic blood pressure
- Temperature (oral preferred, ear or axillary permitted)

- Respiratory rate

A by-subject listing of all vital sign measurements and change from Baseline will be presented by treatment group and time point. The listing will include a flag for values identified as TEMA/PCS as defined by the criteria outlined in [Table 14-7](#).

Descriptive statistics will be reported for all vital sign measurements. Measured values and changes from Baseline will be summarized by vital signs variables and time point for each treatment group. Summarization will be as treated, subjects who missed treatments will not be summarized.

Repeated and unscheduled measurements will be handled as described in [Section 4.3](#).

11.4.2 Electrocardiograms

Standard 12-lead ECG recordings will be taken in triplicate with the subject resting in the supine position for at least 15 minutes and before obtaining any blood samples for assessments of laboratory variables. The following variables will be reported:

- Heart rate
- RR interval
- PQ/PR interval
- QRS duration
- QT interval
- QT corrected for heart rate using Bazett's formula ($QTcB = QT/RR^{1/2}$)
- QT corrected for heart rate using Fridericia's formula ($QTcF = QT/RR^{1/3}$)

The individual measurements and the mean of the triplicate measurements will be reported in the by-subject listings. The listing will include the change from Baseline (based on the mean of the triplicate measurements at each time point) and will be presented by treatment group and time point. The listing will also include a flag for values identified as TEMA/PCS as defined by the criteria outlined in [Table 14-7](#).

Measured values and changes from Baseline will be summarized by treatment group at each time point and by ECG variable (based on the mean of the triplicate values at each time point). Summarization will be as treated, subjects who missed treatments will not be summarized.

Electrocardiogram findings for the individual triplicate measurements will be listed separately.

Frequency counts of normal vs abnormal findings will be presented by treatment group and time point.

Repeated and unscheduled measurements will be handled as described in [Section 4.3](#).

In the event that the complete set of triplicate measurements is not available at a specified time point the data will be handled as described in [Section 4.2.6](#).

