3.2.3 Mapping of assessments performed at Premature End of Treatment Visit

Efficacy and safety assessments at a Premature End of Treatment Visit (PEOT) that correspond to a scheduled visit will be summarized at the next scheduled visit.

In particular, clinical laboratory parameters, vital signs, ECG and exploratory safety biomarkers are assessed at all Treatment Period visits, and so all assessments of these variables at PEOT corresponding to a scheduled visit will be mapped to the corresponding scheduled visit.

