3.5.3 Safety Set

The Safety Set (SS) will consist of all subjects in the RS, who have received at least 1 dose of IMP.

Safety and immunological variables will be analyzed using the SS.

It is expected that subjects will receive treatment as randomized and hence safety analyses will be based on the randomized treatment group. However, if after unblinding it is determined that a subject has received the incorrect treatment based on the randomization schedule, then for safety analyses the subject will be allocated to the actual treatment they received in the respective Dosing Period.

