11 SAFETY ANALYSES

All safety analyses will be presented using the SS. Listings will be presented by Dosing Period, treatment group and subject; tabulations will be presented by Dosing Period and treatment group in the following order:

Dosing Period 1:

- Placebo
- UCB7665 7mg/kg

For Dosing Period 2 and the Observation Period the following treatment groups will be considered for analysis and will be displayed as such in the TFLs (the first two groups will only be utilized for observation period in case patients do not receive any dosing in period 2):

- Placebo
- UCB7665 7mg/kg
- Placebo - UCB7665 7mg/kg
- Placebo - UCB7665 4mg/kg
- UCB7665 7mg/kg - UCB7665 7mg/kg
- UCB7665 7mg/kg - UCB7665 4mg/kg

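### The vital-sign and ECG summaries leave out subjects who 'missed treatments', an undefined exclusion that conflicts with the Safety Set rule and, however it is read, with other SAP rules

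*SAP*

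**What the plan says.** The same sentence stands in SAP 11.4.1 (vital signs) and SAP 11.4.2 (ECG), directly after the plan for tables of measured values and changes from Baseline: "Summarization will be as treated, subjects who missed treatments will not be summarized". Neither section says how many doses make a treatment missed, whether a partial infusion counts, or whether the exclusion covers the whole subject, a Dosing Period, or only later visits.

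Other parts of the SAP set these rules:

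- **Population.** SAP 3.5.3: "Safety and immunological variables will be analyzed using the SS". SAP 11: "All safety analyses will be presented using the SS". The Safety Set needs one dose. The protocol's analysis-set section has the same definition and rule.
- **Early stoppers.** SAP 3.2.3: "safety assessments at a Premature End of Treatment Visit (PEOT) that correspond to a scheduled visit will be summarized at the next scheduled visit". It then names vital signs and ECG among the variables for which "all assessments of these variables at PEOT corresponding to a scheduled visit will be mapped to the corresponding scheduled visit".
- **No Period 2 dosing.** SAP 3.2.2: "All data up to the missed dose will be treated according to plan". SAP 11 lists Placebo and UCB7665 7mg/kg columns with the note that "the first two groups will only be utilized for observation period in case patients do not receive any dosing in period 2".
- **Laboratory data.** SAP 11.3 has no such exclusion: "Chemistry, hematology and coagulation parameters will be summarized by treatment group at each time point, for both absolute values and changes from Baseline".

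Protocol 14.4.1 plans the vital-sign and ECG summaries without an exclusion. SAP 3.9, which lists changes to protocol-defined analyses, covers only MGADL.

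**The concern.** Two programmers could build different tables from this sentence, and both could claim to follow the SAP. The literal version takes dosed subjects out of a safety summary because they stopped dosing.

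Safety and tolerability is a secondary objective, and Dosing Period 1 gives the only placebo-controlled safety comparison. Under Protocol 6.4 some mandatory reasons for stopping IMP are tolerability events, so those removed may differ from those kept. One route is direct. A severe infusion reaction that needs corticosteroid and/or epinephrine therapy stops IMP, and Protocol Table 18.1 gives a systolic change above 40 mmHg as an example sign of a severe reaction. That subject's scheduled blood pressures could be absent from the only table 11.4.1 plans. For ECG, Protocol 14.4.1 puts the focus on outliers and trends, and the trend tables are the ones the clause touches.

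The values will often exist. Protocol 8.5 asks subjects who stop early to attend the Premature End of Treatment (PEOT) visit and encourages them to attend the Observation Period visits.

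**Working it through.** There is no figure in the plan to reproduce. The check sets the possible readings against the other rules and counts what each removes. The documents give no rate of missed doses, so the counts are per subject.

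**Inputs.** Visit schedule: Protocol Table 5.1 and section 8. Vital-sign timing on dosing days: Table 5.1 footnote f (predose, 15 minutes after start, end of infusion, 2 h and 4 h after the end). Planned size: about 42, randomized 1:1 twice (SAP 2.3).

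**Case 1: stops IMP after the Visit 4 dose, PEOT before Day 15 (mapped to Visit 6).** Post-Baseline time points in the placebo-controlled part:

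- Vital signs: Visit 2 after the start of dosing 4 + Visit 4 predose and later 5 + PEOT 1 = 10.
- ECG triplicates: Visit 4 1 + PEOT 1 = 2.

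| Reading of the clause | Vital signs removed | ECG removed | SAP rules contradicted, besides the Safety Set rule |
|---|---|---|---|
| A. Whole subject out after any missed dose | 10 of 10 | 2 of 2 | 3.2.3; also 3.2.2 and the SAP 11 Observation columns for a subject not dosed in Period 2 |
| B. Subject out of a Dosing Period in which any dose was missed | 10 of 10 | 2 of 2 | 3.2.3 |
| C. Subject out of a period in which no dose was received | 0 | 0 | SAP 11 Observation columns |
| D. Only data after the missed dose out | 0 if PEOT precedes the missed dose | 0 if PEOT precedes the missed dose | SAP 11 Observation columns; also 3.2.3 if PEOT follows the missed dose |

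Under D with a later PEOT, the PEOT set itself goes: 1 of 10 and 1 of 2.

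Reading C keeps all Period 1 data, because every Safety Set subject has a Period 1 dose. It still fails in the second part of the tables. SAP 11 puts Dosing Period 2 and the Observation Period under one set of columns, and two of those columns exist only for subjects with no Period 2 dose. Excluding those subjects leaves the columns empty.

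**Case 2: misses only the Visit 13 dose.** Vital-sign visits after Visit 2 are 4, 6, 8, 9, 11, 13 and 15 to 20, which is 12; ECG visits are 4, 6, 8, 9, 11, 13, 15, 18 and 20, which is 9. Reading A removes all of these and the 4 Visit 2 vital-sign readings after the start of dosing. The whole placebo-controlled record goes for a dose missed on Day 43. B, C and D remove nothing from Period 1. D removes up to 6 vital-sign visits (15 to 20) and 3 ECG visits (15, 18, 20) from the Observation Period.

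**Weight of one subject**, assuming equal allocation and that all 42 are dosed and re-randomized: a Period 1 column has 42/2 = 21 subjects, and 1/21 = 4.8%; a Period 2 column averages 42/4 = 10.5, and 1/10.5 = 9.5%.

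**The case against.** The best defence is that the clause is tied to summarization as treated. SAP 3.5.3 allocates mistreated subjects to the treatment received in the respective Dosing Period, and SAP 11 tabulates by Dosing Period. On that view a subject with no treatment in a period simply has no column there, and no Period 1 data are lost. Reading D is also mild, and it fits 3.2.2. It may also be leftover wording: SAP Amendment 1 added the Observation columns for subjects not dosed in Period 2 and does not list this sentence as changed. That is an inference.

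The practical effect may be small too. A severe infusion reaction would appear as a flagged adverse event, and pressures meeting the TEMA/PCS criteria are flagged in the listing. Unscheduled readings after the first dose are left out of descriptive statistics anyway (SAP 4.3). One 40 mmHg excursion among 21 subjects moves a mean by 40/21 = 1.9 mmHg. ECG outliers stay visible in the flagged listing, and the normal/abnormal counts follow the sentence without repeating it.

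Much of this stands. Loss of Period 1 data depends on the reading, and as-treated allocation is itself consistent with the Safety Set rule. But the mild readings do not rescue the clause: C empties columns that SAP 11 provides, and D conflicts with those columns and can conflict with 3.2.3. Leftover wording would explain the sentence, but it would still need removing.

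**Conclusion.** The point holds as an undeclared and undefined exclusion in two sets of safety summaries. Literally it contradicts the Safety Set rule, and no plausible reading agrees with the rest of the SAP. The Case 1 loss ranges from 0 to 10 of 10 vital-sign time points and from 0 to 2 of 2 ECG time points, depending only on how the clause is read.

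A reader might infer that the SAP plans to drop every early stopper from the placebo-controlled comparison, or that it would hide tolerability signals. The documents do not support either. The first follows only under readings A and B. As to the second, stops for withdrawn consent, rescue therapy or prohibited medication need not be tolerability events, so the net direction is unknown. The number of subjects affected is unknown too. Listings with TEMA/PCS flags, ECG normal/abnormal counts, adverse-event, laboratory, exposure and liver-injury outputs are unaffected, as are all efficacy results. It should be corrected, but it does not threaten the trial's main conclusion.

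**What to change.** In SAP 11.4.1 and 11.4.2, delete the part of the sentence after the comma and keep the instruction to summarize as treated. Summarize every Safety Set subject with a value at each time point by treatment received, and show n. Map PEOT values as in 3.2.3, and place subjects not dosed in Period 2 in the Observation columns SAP 11 already defines.

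If an exclusion is really intended, define a missed treatment, state whether the rule works by subject, by Dosing Period or by visit, reconcile it with 3.2.2, 3.2.3, 3.5.3 and 11, and list it in 3.9.

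The cost is SAP wording and minor table programming, with no new data. The downside is that n will vary between visits.
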